#### EXCLUSION CRITERIA

##### 3.2.6 Diagnosis and Treatment

3.2.6.1 Patients with pontine glioma are not eligible.

3.2.6.2 Patients with an estimated survival of less than one year are not eligible.

3.2.6.3 Patients with a history of traumatic brain injury prior to tumor diagnosis are not eligible.

##### 3.2.7 Performance Level

3.2.7.1 Patients with a motor, visual, or auditory handicap that prevents computer use (e.g., unresolved posterior fossa syndrome) are not eligible to participate in this trial.

3.2.7.2 Patients with Full-Scale IQ < 70 per previous testing OR existing diagnosis of/educational classification as a student with an Intellectual Disability are not eligible.

## REGULATORY

- 3.2.8 All patients and/or their parents or legal guardians must sign a written informed consent (patient assent is also recommended when applicable according to each institution's policy).
- 3.2.9 All institutional, FDA, and NCI requirements for human studies must be met.

**4.0 TREATMENT PLAN****4.1 Overview of Treatment Plan**

Our goal is to establish feasibility and preliminary efficacy of this intervention in a small sample of 60 randomized participants. Patients 6-16 years old newly diagnosed with a brain tumor requiring CRT will be identified for participation in this study by the institutional oncologist, nurses, psychologist, or other member of the healthcare team at each participating site. This age range was selected because it includes children who are old enough to be able to complete the intervention, and young enough to be at substantial risk for CRT-related late effects.

Within 2-4 months of completing CRT, enrolled participants will complete baseline measures (see [Section 4.7](#) and [Appendix III](#)). Those who meet criteria for randomization per [Section 4.2](#) will be randomized to the intervention arm or an active control group. Almost all participants are expected to be receiving chemotherapy during this period. Randomization will be stratified by known risk factors including age (< 8 vs.  $\geq$  8), treatment intensity (whole brain vs. focal radiation) and also by Coach (A versus B). Reminder: at enrollment participants will be randomized to receive *Cogmed* coaching from one of two coaches (Coach A or Coach B) according to a block randomization schedule. The patient's coach assignment record can be found on the Eligibility form receipt in eRDES (a field auto-populated by the system after the form has been validated and saved).

The design will be a single-blind, dose-controlled trial in which half of the participants will be randomized to the adaptive intervention condition and half will complete training on a non-adaptive comparison computer program. At each assessment (baseline, post-treatment, and follow-up), the person performing any cognitive testing (i.e., computerized assessment and/or the optional psychologist battery) will be blinded to randomization. Given the role of cognitive-behavioral coaching in the CT program, it will not be possible for coaches to be blinded to participants' randomization status, but coaches will not perform any of the pre- or post-training assessments. In our previous work, we had no difficulty maintaining this blind between coaches and examiners. Parents and participants will be blinded to randomization, at least initially. Because they will have been informed that the two study conditions are distinguished by their difficulty level, some parents and/or children may be able to guess their randomization status. Reminder: if patient starts or changes dosage of psychostimulant medications during the study period, patient will be removed off study.

*Cogmed* (see [Appendix II](#)) is a home-based, computerized, interactive, audio-visual CT program. Designed to be completed over 25 training sessions spanning 5-9 weeks, *Cogmed* consists of twelve engaging exercises that target skills involving visuo-spatial and verbal WM (separate versions of the program are available for preschool- and school-aged children). This CT program is particularly appropriate for the pediatric brain tumor population because of its ease-of-use, ability to be completed at home, and established efficacy in other patient

populations. Primary outcomes will include measures of attention and WM. Of note, participants assigned to the non-adaptive condition will complete a modified version of the computerized CT consisting of tasks that never increase in difficulty. If patients do not complete the training within 9 weeks, they will be removed off protocol therapy (see [Section 5.1](#)).

Participants will be asked to return to the clinic within three weeks of completing the intervention program for brief follow-up testing; ideally this appointment would be scheduled in conjunction with one of their regular clinic visits. Six months following completion of the intervention patients will return to complete another brief assessment to evaluate stability of any changes over time. At that time, following completion of all testing procedures, families will be informed of whether they received the adaptive or non-adaptive intervention (i.e., participants will be unblinded) and families enrolled in the non-adaptive arm of the study will be given the opportunity to complete the adaptive training at no cost and with the support of a Cogmed-certified coach.

#### 4.2 Criteria for Randomization

**Patients must fulfill all criteria listed below to proceed to randomization, otherwise, patient will be off study.**

##### 4.2.1 Timing

The maximum period between the end of radiation and randomization is 4 months.

##### 4.2.2 Criteria

4.2.2.1 Patients with evidence of IQ < 70 (from psychologist administered baseline testing or other cognitive testing) OR existing diagnosis of/educational classification as a student with an Intellectual Disability, will not be eligible.

4.2.2.2 Patients diagnosed with any mental health disorder (e.g., depression, anxiety, oppositional defiant disorder) that, in the treating physician or psychologist's opinion, would preclude or take treatment precedence over participation in CT will not be eligible.

**Reminder:** if a patient starts or changes dosage of a psychostimulant medications, the patient will be taken off study – [See Section 5.2](#).

#### 4.3 Procedures

Three study visits will be required for participation in the study (see [Section 4.7](#)). First is the screening/baseline assessment, which will be conducted for all participants following study enrollment. The baseline testing must be performed within 4 months after the completion of CRT. The two remaining study visits are the post-intervention assessment and the follow-up assessment, which will be needed only for participants who meet criteria for randomization and who are randomized. Screening/baseline assessment may include administration of an abbreviated intellectual test battery, a WM battery, and a computerized attention measure (see [Appendix III](#)). Parents will complete questionnaire measures regarding their child's adaptive, behavioral, emotional, and attentional functioning. Clinical interviewing will be conducted to clarify any potential problems identified on the questionnaires; final decisions about psychosocial eligibility of children will be made by the evaluating psychologist at each site based on all available data. Participants and their parents will each receive a \$15 gift card (or comparably valued prize/compensation) for participation in the screening/baseline assessment. It is anticipated that some children who complete the screening/baseline assessment will not meet randomization criteria based on evidence of

intellectual disability or psychiatric functioning. In the trial of *Cogmed* with survivors, less than 10% of children screened were excluded from participation for these reasons.

Participants meeting criteria for randomization will be trained in the use of the *Cogmed* programs in the clinic by study personnel (see below and [Appendix II](#)). In order to avoid biasing the sample towards socioeconomically advantaged individuals, participants without dedicated access to an adequate home computer will be provided with a laptop computer or tablet device for the duration of the intervention, regardless of whether they are assigned to the adaptive or non-adaptive arms. Moreover, families without available internet access will be provided with wireless internet cards for the duration of the intervention. The intervention will consist of three to five, 15- to 45-minute sessions (younger children practice for less time) per week for 5 to 9 weeks (total = 25 sessions). If patients do not complete the training within 9 weeks, they will be removed off protocol therapy but will remain on study and will receive the post-intervention and follow-up assessment. Similarly, patients who do not complete the 25 sessions for any reason will receive the post-intervention and follow-up assessment unless they meet Off Study Criteria (see [Section 5.0](#) below). Thus, using an intent-to-treat approach, every effort will be made to obtain post-intervention and follow-up data on every child who is randomized, unless they meet Off Study Criteria.

To assist participants as they complete the intervention, a treatment “coach” will be available to parents and children by phone throughout the intervention period. Weekly phone contact with the coaches will be scheduled so that compliance and feasibility data may be collected and so that any problems (e.g., training issues, adverse events, technical problems) can be addressed efficiently. Of note, *Cogmed* routinely provides technical assistance to individuals using the programs at no additional cost. Additionally, to promote compliance and maintain children’s interest in the program, participants will earn \$10 gift cards (or comparably valued prizes/compensation) after completion of approximately each third of the training (total = \$30). This incentive schedule is similar to the one used in the trial of this program in survivors of childhood cancer, and was associated with a compliance rate of 85%.

#### 4.4 Computerized Cognitive Training Treatment

*Cogmed RM* and *Cogmed JM* (see [Appendix II](#)) are computer programs that are installed from a CD-ROM and compatible with most Windows-based computers. They are commercially available to qualified practitioners through *Cogmed*; [name] has already received training and certification as a practitioner and has experience treating children on a previous NCI study (R03-CA132570). The program consists of twelve visually engaging and interesting exercises that target skills involving visuo-spatial and verbal WM. Difficulty of the tasks is automatically adjusted on a trial-by-trial basis throughout each training session to match a child’s current WM such that as the child becomes more proficient, the exercises become more difficult. *Cogmed RM* is designed for children aged 8 to 18 and *Cogmed JM* is the preschool version of the computer program (ages 4 to 7).

Throughout training, the child’s assigned intervention coach has online access to detailed information about his or her training sessions. Specifically, coaches can see when and how long children trained, and the outcome (pass or fail) of each of the 120 trials children complete during a single training session. Using this information, coaches can modify the training sequence or make suggestions to the child and/or parent about how progress can be maximized (e.g., by taking a short break after three failed trials to prevent frustration). Strategies to promote treatment success and compliance are based on cognitive-behavioral principles (e.g., positive reinforcement, self-encouragement, problem-solving). Families will have phone meetings at least once per week with an intervention coach to ensure

compliance, track progress, provide feedback and answer any questions that may have arisen during treatment.

#### 4.5 Neuropsychological and Behavioral Measures

##### 4.5.1 Study Instruments

The instruments used are listed in [Table 1](#) below, and described in [Appendix III](#). If your institution does not have access to all test instruments specified in [Appendix III](#), it may be possible to borrow the test materials. Loaning of test kits will be dependent upon availability. **Please note that only English test kits and materials are available for loan.** At least 3 weeks prior to the date of assessment, contact [REDACTED] with your request for materials.

##### 4.5.2 Baseline Testing, with and without Optional Psychologist Portion

The full list of study assessments to be completed at baseline are presented below in [Table 1](#).

**For sites participating in the psychologist portion (optional):** a brief neuropsychological/behavioral assessment will be conducted at baseline to establish that children are cognitively and psychologically eligible for participation, and in order to document individual and family variables that later may be found to relate to feasibility. Specifically, children will complete neuropsychological measures and a psychiatric interview will be conducted by a study psychologist at each site to determine whether the child meets criteria for any DSM-5 mental health disorder that, in the psychologist's opinion, would contraindicate participation in the intervention. For example, a child with significant performance anxiety may be excluded if the evaluating psychologist feels that study participation was likely to increase the child's anxiety during training. Thus, the intent would be to avoid enrolling children for whom cognitive training may exacerbate existing, clinically significant mood or behavioral symptoms. The baseline assessment will require 60-90 minutes.

**Note that, if a site is not participating in the optional psychologist-administered battery, a member of the child's medical or psychosocial support team may provide approval for the child to participate in the study, based on available information about the child's current or prior mental health.** [name] may be contacted prior to participant enrollment with any questions about what parameters should be considered before approving a child for participation.

##### 4.5.3 Post-Intervention and 6-month Follow-up Assessments

**CogState**, a brief, computerized assessment of memory functioning will be administered following the intervention (at approximately 5 months post-CRT) and again 6 months following the completion of the intervention. The computerized testing can be administered by any individual who completes online training for CogState or who has already completed online training for any of the other COG trials for which CogState has been used (i.e., AAML1331, AALL1131, ACCL0922). Parents/caregivers will also be asked to complete the BRIEF and the Feasibility Interview at these timepoints. Testing will require approximately 20-30 minutes at each timepoint. The child will also complete the Feasibility Interview

at the post-intervention assessment, and the parent will complete the Computer Use questionnaire and ABAS-3 at the 6-month follow-up.

**Optional Testing:** It is highly recommended that the psychologist-administered measures also be administered, if possible, following the intervention (at approximately 5 months post-CRT) and again 6 months following the completion of the intervention. Measures were selected to be compatible with COG ALTE07C1, when possible, in order to be consistent with the Behavioral Science Committee's resolution to streamline assessments, promote higher compliance with neurocognitive study aims, reduce costs, and increase the ability to compare findings across COG-supported studies. The psychologist-administered post-intervention assessments will require about 30 minutes each. At each institution, a psychologist or neuropsychologist will oversee this optional testing.

#### 4.6 Feasibility Interview

For a previous trial with survivors of childhood cancer (R03-CA132570), a 13-item survey (see [Appendix VA](#) and [VB](#)) for parents and children was developed and utilized to assess technical feasibility, adherence, satisfaction, and ease-of-use. The Feasibility Interview will be completed by the parent by phone following Session 12. Additionally, both child and parent will complete a second interview during the post-intervention assessment. See [Table 1](#) below.

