### 6.3.3 Analysis Plan

Compliance rate (the portion of patients who complete at least 80% of the sessions within 9 weeks) will be calculated for the overall study population and each arm separately. Z-test for binomial proportion with continuity correction will be used to examine if the overall compliance rate is lower than the target of 75%. Confidence intervals of the estimated compliance rate will be constructed for the overall study population and for each arm separately. We will use Fisher's exact test to examine if there is any significant difference in the compliance rate between the 2 arms. Compliance data on the number of sessions completed for all patients and for patients on each arm will also be described by summary statistics such as mean or median, and compared between the 2 arms by two-sample t-test or Wilcoxon rank sum test. We will use descriptive and summary statistics to report parent and child ratings of the intervention's technical feasibility, ease-of-use, and satisfaction across the three time-points that this information is collected. In addition, we will use descriptive and summary statistics to detail the total number of patients enrolled, determine rates and reasons for non-eligibility and patient refusal for randomization, characterize socioeconomic status of the parents and computer usage for the patients and evaluate the number and type of adverse incidents reported through the questionnaires (if any). We will use a series of t-tests (for continuous variables) and Chi-square tests or Fisher's exact tests (for non-continuous variables) to examine potential differences between eligible patients who accept or decline to be randomized to the treatment phase, between participants who are compliant (i.e., 80% of sessions completed) and noncompliant, and for other medical, psychosocial, and contextual factors.

The analysis of preliminary efficacy will be conducted on an intent-to-treat basis. We will use descriptive/summary statistics to summarize the objective and the subjective measures of attention and WM in each arm and the differences between the 2 arms on the post-intervention/6-month assessment or on the difference between the post-intervention/6-month assessment and the baseline assessment. Linear regression models using the post-intervention/6-month assessment as outcome will also be used to estimate the effect size of intervention with adjustment for potential confounders including the baseline assessment. Linear

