## APPENDIX VA: PARENT FEASIBILITY AND ACCEPTABILITY INTERVIEW

### Obtain Following CT Session 12 and After Training Completion

Subject: \_\_\_\_\_

Subject ID: \_\_\_\_\_

Date: \_\_\_\_\_

Session: 12 25

Respondent: \_\_\_\_\_

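### The mid-training parent Feasibility Interview is triggered only by reaching session 12, so that wave leaves out, by rule, every family that stops sooner

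*Combined protocol and SAP*

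**What the plan says.** Section 4.6 gives the timing of the first parent interview: "The Feasibility Interview will be completed by the parent by phone following Session 12". It then adds: "Additionally, both child and parent will complete a second interview during the post-intervention assessment". Table 1 in Section 4.7 shows the same two occasions. The parent form in Appendix VA is headed "Obtain Following CT Session 12 and After Training Completion", and its session field offers only 12 or 25. The child form in Appendix VB is likewise headed for use once training is complete.

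Section 4.3 covers children who do not finish. Of those who run past 9 weeks it says "they will be removed off protocol therapy but will remain on study and will receive the post-intervention and follow-up assessment", and more generally that "patients who do not complete the 25 sessions for any reason will receive the post-intervention and follow-up assessment unless they meet Off Study Criteria". It adds that "every effort will be made to obtain post-intervention and follow-up data on every child who is randomized", again short of the off-study criteria. It also plans calls outside the interview: "Weekly phone contact with the coaches will be scheduled so that compliance and feasibility data may be collected".

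Section 1.1 puts reported ease-of-use and satisfaction in the primary feasibility hypothesis, and Section 6.3.1 makes the interview items secondary feasibility endpoints. Section 6.3.3 summarises the ratings descriptively, including "satisfaction across the three time-points that this information is collected". It gives no denominator and no rule for interviews that were not obtained.

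**The concern.** Entry to the mid-training wave depends on adherence, and adherence is the primary outcome. A child who stops at session 3 or session 10 never reaches the trigger, so the parent is not asked at that stage about technical problems, resistance or frustration. These are plausible reasons for stopping. The mid-training summary may therefore look better than the experience of all randomised families. Section 6.3.3 does not require the report to say how many families are behind it or who is absent. In a study meant to show whether families can manage the training, and so to inform a larger trial, the omitted group is the one whose answers are most needed.

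**Working it through.** **Who is interviewed, and when**

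- *Stops before session 12.* No mid-training interview. The post-intervention interview is still due under Section 4.3, unless the child is off study.
- *Stops at sessions 12 to 19.* Non-compliant on the primary endpoint (fewer than 20 sessions), but the mid-training interview has been triggered and the post-intervention one is due.
- *Reaches 20 or more sessions.* Both are due.

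The exclusion by rule is thus confined to one wave and to stops before session 12. Refusing further training and exceeding 9 weeks appear in Section 5.1 (removal from protocol therapy), not in Section 5.2 (off study), so neither cancels the later interview.

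**The plan's own figures**

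The plan gives no figure for the interview. Its design figures reproduce and do not depend on it.

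- Critical value: 0.75 − 1.645 × √(0.75 × 0.25 / 60) − 1/(2 × 60) = 0.6497.
- Power at 59%: Φ[(0.6497 − 0.59) / √(0.59 × 0.41 / 60)] = 0.827, against 0.82 stated.
- Enrolment: 60 / 0.85 = 70.6, rounded up to 71, as stated.

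**Illustration for the mid-training wave**

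Inputs: 60 evaluable participants and a 75% target (Section 6.3.2); 94.4% of parents satisfied in the earlier survivor trial (Section 2.3.2), used here for families who reach session 12. Assumptions: one third to two thirds of non-compliant families stop before session 12, and 50% of those are satisfied.

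- Non-compliant at the target: 0.25 × 60 = 15. One third to two thirds is 5 to 10 families, or 8% to 17% of 60.
- All families, 5 missed: (55 × 0.944 + 5 × 0.50) / 60 = 0.907.
- All families, 10 missed: (50 × 0.944 + 10 × 0.50) / 60 = 0.870.
- The mid-training wave shows 0.944 in both cases, which is 3.7 to 7.4 points too high for the whole group.

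More generally, the tilt is f × (0.944 − s), where f is the share stopping before session 12 and s is the satisfaction of those families.

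| f | s = 70% | s = 50% | s = 30% |
|---|---|---|---|
| 10% | 2.4 points | 4.4 | 6.4 |
| 20% | 4.9 | 8.9 | 12.9 |
| 25% | 6.1 | 11.1 | 16.1 |

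The 25% row is the extreme at the target rate, where all 15 non-compliant families stop before session 12.

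**Post-intervention wave**

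Take f = 20% and s = 50%, so the true figure is 0.80 × 0.944 + 0.20 × 0.50 = 0.855. Let r be the share of early stoppers interviewed, with all other families interviewed. The observed figure is (0.80 × 0.944 + 0.20 × r × 0.50) / (0.80 + 0.20 × r).

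- r = 1: 0.855, tilt 0.
- r = 0.5: 0.895, tilt 3.9 points.
- r = 0: 0.944, tilt 8.9 points.

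**Number of time-points**

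Section 4.5.3 asks parents for the interview at post-intervention and again at 6 months. With session 12 that makes three, which agrees with Section 6.3.3. Section 4.6, Table 1 and Appendix VA give two and show no 6-month interview.

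**The case against.** A reader might infer that the ease-of-use and satisfaction results as a whole favour families who kept training. The documents do not support that. The same parent form is due at post-intervention, Section 4.3 extends that visit to non-completers, and Section 4.5.3 adds a 6-month parent interview. If Section 4.3 is followed, the post-intervention tilt is zero. That early stoppers will attend less often is a reasonable expectation, not something the documents show.

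A reader might also infer that the reasons for stopping will go unrecorded. The weekly coach calls do not depend on session count, and Appendix II gives them a script covering factors related to feasibility. Nor does it follow that an interview with a non-completer could not be coded: the form has a date field, the 25 may simply label the post-training occasion, and the case report forms are held elsewhere. Finally, a fixed session-12 reading compares families at equal exposure, which has value, and no decision rule rests on it.

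All of this limits the point without removing it. The coach calls do not yield the interview items that Section 6.3.1 names as endpoints. The later interview is an imperfect replacement: the parent form asks about resistance and satisfaction over the current month, which for a child who stopped in week 2 may contain no training. Section 4.1 times the visit from completion of the programme, a date that an early stopper does not have. Form headings that refer to completed training could lead a site to pass over the non-completers whom Section 4.3 means to include.

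**Conclusion.** The point holds for the session-12 wave. Families who stop before session 12 are excluded from it by rule, and its ratings describe only those who reached session 12. Under the stated assumptions the overstatement is about 4 to 7 points, and about 2 to 16 points across the wider table. The share stopping early and their satisfaction are assumptions, and the 94.4% is borrowed from a different population, so these figures show scale and are not predictions. The base of 60 is evaluable participants, after medical removals, and so is not every randomised family.

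The post-intervention wave is sound as designed and is at risk only in execution, a risk that the form wording raises. The primary compliance endpoint is untouched. This is an inexpensive improvement to a secondary endpoint, plus an inconsistency in the number of interviews that needs to be settled.

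**What to change.** 1. In Section 4.6, Table 1, Appendix III and Appendix VA, trigger the mid-training parent interview after session 12, at a fixed time after the first session (for example 5 weeks), or when the family stops training, whichever comes first. Give it by phone around the weekly coach call. At the slowest planned pace (25 sessions in 9 weeks) session 12 falls at 12/25 × 9 = 4.3 weeks, so a 5-week limit would reach only families who are behind schedule.
2. On the parent form, replace the choice of 12 or 25 with the actual number of sessions completed.
3. Reword the headings of both the parent form (Appendix VA) and the child form (Appendix VB) to match Section 4.3, so that non-completers are plainly included.
4. In Section 6.3.3, report for each wave the number randomised, the number interviewed and the ratings, split by whether session 12 was reached.
5. Reconcile Sections 4.5.3 and 6.3.3 (three time-points, including a 6-month parent interview) with Section 4.6, Table 1 and Appendix VA (two).

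The cost is wording in a few places and one form field, using phone contact already planned. Some interviews will reflect fewer than 12 sessions of experience; the split in item 4 keeps the session-12 reading separate. Families who withdraw consent or cannot be reached will still be missing, but the report will show how many.
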